3.8. Other Analyses

3.8.1. Patient Reported Outcomes

[Redacted text block containing multiple paragraphs of patient reported outcomes data, all content obscured by black bars.]

total number with problems at baseline

[REDACTED]

[REDACTED]

[REDACTED]

[REDACTED]

[REDACTED]

[REDACTED]

[REDACTED]

[REDACTED]

[REDACTED]

[REDACTED]

[REDACTED]

[REDACTED]

3.9. Interim Analyses

The study will have an interim freeze to perform the primary analysis after the last subject reaches the Week 12 timepoint or discontinues prior to Week 12.

3.9.1. Maintenance of blind following interim analysis

Study team members with access to subject level during the interim analysis that reveals a subjects dose (i.e. 80mg or 200mg) during the ATE period cannot participate in study-related activities from that point on. Full details on maintenance of the blind and who has access to subject level data are detailed in the study unblinding plan.

3.9.2. Data Monitoring Committee

[REDACTED]

5. SUPPORTING DOCUMENTATION

5.1. Changes to Protocol-Planned Analyses

5.2. CDAI Questionnaire

Subscore	Definition	Multiplier
Number of liquid or very soft stools	Number of liquid or very soft stools (7 day total) Note: Liquid or very soft stools are entered as Type 6 and Type 7 in the patient diary	x 2
Abdominal pain	Abdominal pain (7 day total) Daily scores calculated as (0=none, 1=mild, 2=moderate, 3=severe)	x 5
General well-being	General well-being (7 day total) Daily scores calculated as (0=generally well, 1=slightly under par, 2=poor, 3=very poor, 4=terrible)	x 7
Extra-intestinal manifestations	Arthritis/arthralgia (yes=1, no=0)	x 20
	Iritis/uveitis (yes=1, no=0)	x 20
	Erythema nodosum, pyoderma gangrenosum, aphthous stomatitis (yes=1, no=0)	x 20
	Anal fissure, fistula, or abscess (yes=1, no=0)	x 20
	Other fistula (yes=1, no=0)	x 20
	Fever over 37.8C (100F) during past 7 days (yes=1, no=0)	x 20
Any anti-diarrhea	Any anti-diarrhea medication in the last 7 days (yes=1, no=0)	x 30
Abdominal mass	Abdominal mass (None=0, Questionable=2, Definite=5)	x 10
Haematocrit (%)	If male, (47 – local hematocrit) [note: if negative impute with 0] If female, (42 – local hematocrit) [note: if negative impute with 0]	x 6

Body Weight	[(ideal weight – current weight) x 100]/ ideal weight [note: if < -10 impute with -10]	x 1
Final Score	Add totals:	

5.3. Data Conventions and Transformations

5.3.1. Derived and Transformed Data

5.3.1.1. Study Day

If the date of interest occurs on or after the first dose/randomization date then study day will be calculated as (date of interest – date of first dose/randomization) + 1.

If the date of interest occurs prior to the first dose/randomization date then study day will be calculated as (date of interest – date of first dose/randomization).

There is no Study Day 0.

5.3.1.2. Change from Baseline

Change from baseline is calculated as (postbaseline result – baseline result).

Percent change from baseline is calculated as ((change from baseline/baseline result) × 100) or equivalently as 100(postbaseline value/baseline value - 1).

If either the baseline or the postbaseline result is missing, the change from baseline and percentage change from baseline values are missing.

5.3.1.3. BMI

BMI is calculated as:

$$BMI (kg / m^2) = \frac{weight (kg)}{height (m)^2}$$

5.3.1.4. Ideal Body Weight

Ideal body weight is calculated as follows (Devine 1974):

- 50 kg + 2.3 kg for each 2.54 cm (1 in) over 152.4 cm (5 ft), if male
- 45.5 kg + 2.3 kg for each 2.54 cm (1 in) over 152.4 cm (5 ft), if female

This is a conversion to metric units of the following simple rule:

- For women, allow 100 lb for the first 5 feet and 5 lb for each additional inch.
- For men, allow 110 lb for the first 5 feet and 5 lb for each additional inch.

5.3.1.5. Creatinine Clearance

Creatinine clearance (mL/min) will be estimated using the Cockcroft-Gault equation, as follows:

$$\begin{aligned} \text{Estimated creatinine clearance (mL/min)} = & \frac{(140 - \text{Age}) \times \text{Ideal Body Weight (kg)}}{72 \times \text{Serum Creatinine (mg/dL)}} \text{, if male} \\ & \frac{(140 - \text{Age}) \times \text{Ideal Body Weight (kg)}}{72 \times \text{Serum Creatinine (mg/dL)}} \times 0.85 \text{, if female} \end{aligned}$$

Creatinine clearance will also be estimated using actual body weight in the Cockcroft-Gault equation above. In tables, figures, and listings, estimates using actual body weight (ABW) will be labeled “Creatinine Clearance - ABW.”

5.3.1.6. Time Since Crohn’s Disease Diagnosis

Time since CD diagnosis (years) as of the first dose date is calculated as (diagnosis date - first dose date)/365.25. It is left unrounded for calculation of summary statistics but rounded to 1 decimal place for display.

5.3.1.7. Prior Biologic Failure

Subjects who have entered primary or secondary non-response and/or intolerance to a biologic treatment on the Prior Crohn’s Disease Medications page are defined as failing prior biologic treatment. All other subjects regardless of receiving prior biologic treatment are not considered failures.

5.3.1.8. Prior Biologic Classes

Anti-tumor necrosis factor-alpha therapies:

- Adalimumab
- Certolizumab
- Infliximab

Anti-integrin therapy:

- Vedolizumab

Anti-interleukin-12 and interleukin-23 therapy

- Ustekinumab

5.3.1.9. Presence of extra-intestinal manifestations

Subjects who have any extra-intestinal manifestations ongoing at baseline as collected in the electronic tablet at site will be categorized as having a presence of extra-intestinal manifestations.

5.3.2. Missing Date Imputation

5.3.2.1. Missing/Incomplete AE/Start Date

Imputation of dates with missing day and/or month is only applied to TEAEs. TEAE start dates with missing day or month will be imputed as follows:

- If day and month are missing but year is available, then the imputed day and month will be 01 Jan or the initial treatment date if they have the same year, whichever is later (because TEAE onset is not expected prior to administration of study treatment)
- If day is missing but the month and year are available, then the imputed day will be the first day of the month or the initial dosing date if they have the same month and year, whichever is later.

5.3.2.2. Missing/Incomplete AE/Medication End Date/Time

Imputation of dates with missing day and/or month is only applied to TEAEs when AE duration is calculated. TEAE end dates with missing day or month will be imputed as following:

- If day and month are missing but year is available, then the imputed day and month will be 31 Dec [with a time of 23:59 if applicable] or the study exit date if they have the same year, whichever is earlier
- If day is missing but the month and year are available, then the imputed day will be the last day of the month or the study exit date if they have the same month and year, whichever is earlier.

5.3.2.3. Missing/Incomplete Start for Medication

To determine whether medications were used prior to initiation of dosing and whether they were used after initiation of dosing, missing or partial dates for medications will be imputed according to the following rule:

Missing medication start date/time:

- If day and month are missing but year is available, then the imputed day and month will be 31 Dec [with a time of 23:59 if applicable] or the study exit date if they have the same year, whichever is earlier.
- If day is missing but the month and year are available, then the imputed day will be the first day [or 1 minute after midnight if applicable] of the month or the first dose date if they have the same month and year, whichever is later.
- If day, month and years are completely missing, impute as date and time of first dose if 1) end date is not missing and occurs on and after date of first dose, or 2) end date is missing but marked as “ongoing”.

5.3.3. Laboratory Data

For non-efficacy laboratory data, a missing baseline value will be replaced with the last available assessment, generally the screening assessment. A retest value will be used if the original test result is invalid, eg, specimen hemolyzed.

Laboratory data that are continuous in nature but are less than the lower limit of quantitation/limit of detection (LOD) will be, in general, imputed as follows:

- A value that is 1 unit less than the LOD will be used for calculation of descriptive statistics if the data are reported in the form of “< x” (x is considered as the LOD). More specifically, x-1 is used for data summarization if the data are reported in the form of “< x”; and x.e where e = d-1, will be used for analysis if the data are reported in the form of “< x.d”; Note:

Laboratory data that are continuous in nature and above the upper limit of quantitation/limit of detection (LOD) will be, in general, imputed as follows:

- A value that is 1 unit less than the LOD will be used for calculation of descriptive statistics if the data are reported in the form of “> x” (x is considered as the LOD). More specifically, x+1 is used for data summarization if the data are reported in the form of “> x”; and x.e where e = d+1, will be used for analysis if the data are reported in the form of “> x.d”;

5.3.4. AE Severity

Instructions:

- AE severity should be provided through data cleaning process as much as possible. If AE severity is not available because a subject was lost to follow-up, sample text for the data imputation is provided below.

For graded adverse event summaries, AEs with no grade reported will be graded as severe.

5.4. Adverse Event Start and End Date/Time Imputation Rules

Missing start date and times will be handled as follows:

- AE onset date completely missing:
 - If AE is not ongoing and AE onset date missing and AE end date missing, then impute AE onset as date/time of first dose.
 - Else if AE is not ongoing and AE onset date missing and AE end date not missing and date/time of first dose <= AE end date, then impute AE onset as date/time of first dose of study drug.
 - Else if AE is not ongoing and AE onset date missing and AE end date not missing and AE end date is BEFORE first dose of study drug, then impute AE onset as AE end date YEAR and MONTH with 01 as the day and 00:00 as time.

- Else if AE IS ongoing and AE onset date missing, then impute AE onset as date/time of first study drug dose.
- AE onset date has year and month only:
 - If AE onset date has year and month only and they are the year and month of first dose of study drug, then impute AE onset as date/time of first dose:
 - Else if AE onset date has year and month only and date/time of first dose is not missing, then impute AE onset as AE onset year and month with 01 as the date and 00:00 as the time.
- AE onset date has year only:
 - If AE onset date has year only and it is year of first dose of study drug, then impute AE onset as date/time of first dose of study drug.
 - Else if AE onset date has year only and date of first study drug dose is not missing and year of AE onset is NOT the year of first dose of study drug, then impute AE onset as Jan. 1 of the AE onset year and 00:00 as the time.
- AE onset missing (where it was not handled by the above cases):
 - If AE onset date is missing, then impute AE onset as date/time of first study drug dose.
- AE onset has complete date but missing time:
 - If AE onset date is a date only and is same as date of first study drug dose, then impute AE onset as date/time of first study drug dose:
 - Else if AE onset date is a date only and is NOT = date of first study drug dose, then impute AE onset as AE onset date with 00:00 as the time:

Missing end date and times will be handled as follows:

- AE end date - completely missing:
 - If AE if not ongoing and both AE onset and AE end dates are missing, then impute AE end date as date/time of last study drug dose.
 - Else if AE is not ongoing and AE onset date not missing and AE end date missing AND AE onset date <= date/time of last dose, then impute AE end date as date/time of last study drug dose.
 - Else if AE is not ongoing and AE onset date is not missing and AE end date is missing and date of last dose is not missing and AE onset is AFTER date of last dose, then impute AE end date as the last day of the month of AE onset date, with 23:59 as time.
- AE end date = year and month only:
 - If AE is NOT ongoing and AE end date consists of year and month only, then impute AE end date as the last day of the month of AE end date month and year, with 23:59 as time.
- AE end date = year only:

[figure not shown]
- If AE is NOT ongoing and AE end date consists of a year only, and year = year of AE onset and AE onset date <= date of last study drug dose, then impute AE end date as the date of last study drug dose.
- Else if AE is NOT ongoing and AE end date consists of a year only, and year = year of AE onset and AE onset date > date of last study drug dose, then impute AE end date as the year and month of AE onset, with the last day of the month as the day, and 23:59 as the time.

- AE end date = complete date but no time:

If AE is NOT ongoing and AE end date consists of a complete date but no time, then impute AE end date = trim(AE end date) || "T23:59".

[REDACTED]

[REDACTED]

[figure not shown]
[Redacted text block 1]

[figure not shown]
[Redacted text block 2]

[Redacted text block 3]

[figure not shown]
[Redacted text block 4]

[Redacted text block 5]

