6. STUDY PROCEDURES

Study procedures will be performed only after written informed consent is obtained. The Screening visits (i.e., Stage 1 and Stage 2) will be performed within 35 days before dosing. One repeat Screening Stage 1 visit is allowed for each subject per the investigator's discretion. No more than one repeat Screening Stage 1 visit or repeat visit-specific procedure/assessment is allowed for each subject, unless prior written approval has been provided by the Sponsor. If the subject does not begin Induction treatment within this 35-day window, Screening evaluation procedures (i.e., Stage 1 and Stage 2) must be repeated. Subjects may be considered for re-screening of both Screening Stage 1 and Screening Stage 2 procedures, depending on the reason for the initial screening failure, per consultation with and approval from the Sponsor.

During the study, every effort should be made to perform study procedures as listed in the Schedule of Study Procedures (Table 1). Assessments will be made and biological samples will be taken in the following recommended order at those study visits at which they coincide: fecal sample collection, adverse event assessment, ECG, vital signs, [REDACTED] clinical laboratory safety samples, [REDACTED] and ileocolonoscopy with biopsies (although ileocolonoscopy should be done within 3 days prior to the Week 12 clinic visit). Study drug administration will be in-clinic on Day 1, Week 4, Week 8, Week 12, ATE Week 16, ATE Week 24, ATE Week 36, and ATE Week 48 after all pre-dose assessments [REDACTED] and procedures have been completed.

Throughout the study, the acceptable window for scheduled assessments is as follows:

- - 3 to + 5 days from the nominal visit date for Week 4, Week 8, ATE Week 4, ATE Week 8, ATE Week 16, ATE Week 24, ATE Week 36, ATE Week 48 and the EOS visits
- -1 to +3 days from the nominal Week 12 clinic visit for the Week 12 ileocolonoscopy with biopsies. The Week 12 ileocolonoscopy and biopsies should be performed on the same day as the Week 12 visit, preferably in the early morning, to permit morning dosing with study drug. However, if not feasible to perform both the ileocolonoscopy and the clinic visit on the same day, the ileocolonoscopy could be performed within 3 days after the Week 12 clinic visit. However, the Week 12 endoscopy must be performed at least 1 day prior to ATE Day 1.
- + 3 days from the nominal visit date for the Week 12 clinic visit

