3.7.2. Adverse Events

Adverse events (AEs) will be coded to the preferred terms (PT) of the Medical Dictionary for Regulatory Activities (MedDRA®). Summaries for induction period and for the complete study period will be presented separately and by system organ class (SOC), preferred term, and severity and/or relatedness, the number and percentage of subjects for whom events were reported.

Adverse events (AEs) are recorded from signing of the informed consent form through the final follow-up assessment. Adverse events observed prior to first dose are non-treatment emergent.

All summaries will be presented for both the Induction Period and the overall study period separately.

Treatment emergent adverse events are defined as follows for induction period and overall:

- Induction period TEAEs are events with a start date/time after the first dose date/time in Induction period up to the date/time of ATE Day 1 dose or date of last dose of study drug + 28 days, whichever is earlier.
- TEAEs for the whole study and listings are defined as AEs with onset on or after the first initiation of study drug up to the date of last dose study drug + 28 days.

Only treatment-emergent AEs will be summarized in the tables. Separate by-subject listings of all TEAEs and all non-TEAEs will be provided.

An AE will be considered a treatment-emergent serious AE (TESAE) if it is a TEAE that additionally meets any SAE criteria.

If more than 1 AE is coded to the same preferred term for the same subject, the subject will be counted only once for that preferred term using the most severe and most related occurrence for the summarizations by severity and by relationship to study drug.

Summary tables will also be provided for Induction period and overall for subjects with:

- TESAEs by SOC and PT
- TEAEs leading to discontinuation of study drug by SOC and PT
- Drug related TEAEs by SOC and PT
- TEAEs by severity and by SOC and PT
- TEAEs resulting in death by PT

Listings of all AEs, SAEs, and AEs leading to premature study drug discontinuation by subject will be presented.

An overall summary of adverse events will also be presented and will include the following summary lines: Any AE, Moderate or Severe AEs, AEs Related to Study Drug, Moderate or Severe AEs Related to Study Drug, Serious AEs, Serious AEs Related to Study Drug, AEs Leading to Premature Study Drug Discontinuation, AEs Leading to Temporary Interruption of Study Drug, and Deaths During Study.

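### SAP 5.4 sets a partly known AE onset to first dose without checking the end date, so an event that resolved before dosing can be counted as a whole-study TEAE

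*SAP*

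**What the plan says.** SAP 5.4 treats an incomplete onset date in three ways.

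- **Completely missing.** The end date is consulted. If the "AE end date is BEFORE first dose of study drug, then impute AE onset as AE end date YEAR and MONTH", with day 01, so the event stays before dosing.
- **Year and month only.** If "they are the year and month of first dose of study drug, then impute AE onset as date/time of first dose". There is no condition on the end date.
- **Year only.** If "it is year of first dose of study drug, then impute AE onset as date/time of first dose of study drug". Again there is no condition on the end date.

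SAP 5.3.2.1 gives a second rule for AE start dates. It opens with "Imputation of dates with missing day and/or month is only applied to TEAEs", and then, for a missing day, "the imputed day will be the first day of the month or the initial dosing date if they have the same month and year"; the later of these two dates applies. It has no end-date check either.

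For medications, the month-only rule in SAP 5.3.2.3 sets the start to the first day "of the month or the first dose date if they have the same month and year, whichever is later".

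On classification, SAP 3.7.2 says that events observed before first dose are not treatment-emergent. It defines whole-study TEAEs by onset on or after first dose, and Induction TEAEs by a start after the first dose date/time. Protocol 8.8.2 uses on or after.

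**The concern.** A recorded end date before first dose settles that the event is pre-treatment, whatever the onset day was. SAP 5.4 uses that information when nothing is known about the onset and ignores it when the month or year is known. The poorer record is classified correctly and the better one is not.

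Such events will be in the database: "Adverse events (AEs) are recorded from signing of the informed consent form through the final follow-up assessment", and "The Screening visits (i.e., Stage 1 and Stage 2) will be performed within 35 days before dosing". That window includes bowel preparation, ileocolonoscopy and biopsies, and Protocol 7.1.1 counts complications of protocol-mandated procedures as AEs.

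What is at stake is the accuracy of the overall-study TEAE tables. The Induction tables, which hold the only placebo-controlled safety comparison, are at stake only if the programmer uses on or after. For medications, a drug stopped before dosing can appear as concomitant under SAP 3.2.5.

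**Working it through.** The plan states no figure on this point, so the check applies the rules as written.

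**1. One example.** First dose 20 Mar 2020, event resolved 12 Mar 2020.

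| Onset as recorded | Rule | Imputed onset | Imputed onset minus end date | Whole-study TEAE? |
|---|---|---|---|---|
| Completely missing | 5.4, end date checked | 1 Mar | −11 days | No |
| Mar 2020 | 5.4, no check | 20 Mar | 20 − 12 = +8 days | Yes |
| 2020 | 5.4, no check | 20 Mar | +8 days | Yes |
| Mar 2020 | 5.3.2.1, later of 1 Mar and 20 Mar | 20 Mar | +8 days | Yes |

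**2. Which TEAE tables.** The imputed onset equals the first dose date/time exactly.

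- Whole-study definition (onset ≥ first dose): counted.
- Induction definition read literally (start > first dose): not counted.
- Protocol 8.8.2 definition (≥): counted.

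The literal Induction wording would also drop events that 5.4 rightly places at first dose. With an onset of Mar 2020 and an end on 25 Mar, the imputed onset is first dose and the event is still not an Induction TEAE.

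**3. Does 5.3.2.1 cure it?** No. Its scope is TEAEs, but by the definitions in 3.7.2 TEAE status depends on the onset date being imputed. It lacks the end-date check too. And 5.4 itself imputes onsets for events that ended before dosing, so such events have not been screened out beforehand.

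**4. Medications.** With first dose 20 Mar, a drug with start Mar 2020 and stop 12 Mar gets a start of max(1 Mar, 20 Mar) = 20 Mar. SAP 3.2.5 counts a start on or after the first dose date as concomitant.

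**5. How often the rule misfires, given such a record.** Inputs: a 35-day screening window (Protocol 6), and 731 consecutive first-dose dates (2020–2021, an assumption). For each first-dose date, take every pair with onset on Day −35 to −1 and end on or after onset but before the dosing day. That is 35 × 36 / 2 = 630 pairs, and 630 × 731 = 460,530 combinations. A combination is misclassified when the onset month (or year) matches that of first dose.

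- Month-year onset: 113,114 / 460,530 = 24.6%.
- Year-only onset: 430,710 / 460,530 = 93.5%.

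The month-only share depends on event length. For fixed lengths the number of combinations is (36 − length) × 731:

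| Event length | Month-year onset | Year-only onset |
|---|---|---|
| 3 days | 9,384 / 24,123 = 39% | 22,869 / 24,123 = 95% |
| 7 days | 6,892 / 21,199 = 33% | 19,981 / 21,199 = 94% |
| 14 days | 3,455 / 16,082 = 21% | 15,004 / 16,082 = 93% |

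**6. With the end-date check added to both partial-date branches.** Misclassified combinations fall to 0 of 460,530 for each type. The event ending on 25 Mar is unchanged.

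**The case against.** - **Setting a doubtful onset to first dose is the usual conservative convention.** That is right when timing is in doubt. A recorded end before dosing removes the doubt, and the completely-missing branch of 5.4 already accepts this.

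- **SAP 3.7.2 already settles the class.** An event that ended before dosing was plainly observed before dosing, so a programmer could apply that sentence first and never impute. This has force: it turns the problem into a conflict of precedence. But nothing ranks 3.7.2 above 5.4, and 5.4 is the explicit algorithm.

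- **The Induction definition excludes an onset equal to first dose.** This stands. Read literally, the randomized safety comparison is untouched.

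- **Such records will be rare.** This also stands. AEs are reviewed at Screening Stage 1, Stage 2 and Day 1, Protocol 7.3 requires onset dates, and an event tied to a dated ileocolonoscopy is among the least likely to lack one. A year-only onset within 35 days of dosing should be rarer still.

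Three stronger readings are not supported.

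- A reader might infer that a false Day 1 start for a corticosteroid or aminosalicylate triggers intercurrent event 4 and turns a responder into a failure. The stated purpose of 5.3.2.3 is only to sort use before from use after the start of dosing, and nothing visible says that intercurrent events are dated with it. Inclusion criteria 107 and 110 leave little room for a short corticosteroid course just before dosing. The primary estimand follows treatment policy, so the primary result could not change.
- A reader might expect negative durations in the TEAE tables. None of the tables listed in SAP 3.7.2 shows duration.
- A reader might apply the calendar overlap of every onset day in screening with the dosing month or year. That includes events not yet over at first dose, for which the rule does no such harm.

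**Conclusion.** SAP 5.4 is wrong as written, and the matter is minor. An AE with a month-only or year-only onset matching first dose, and a recorded end before dosing, is given an onset after its own resolution and counts as a whole-study TEAE, against the intent of SAP 3.7.2. Induction tables share the error only if coded on or after. The month-only rule in 5.3.2.3 misplaces medications in the same way.

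The shares of about 25% and 94% assume equal weight for every date pair and are conditional on a partly dated event that resolved before dosing. They do not forecast how many AEs are affected. The documents do not give that number. It is probably small and, under the blind, similar across arms. No efficacy conclusion depends on it.

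**What to change.** 1. In both partial-date branches of SAP 5.4, add: *If the AE end date is before first dose, impute onset as the first day of the known onset month (or, if only the year is known, the first day of the end-date month within that year, otherwise 1 January of the onset year). The imputed onset may never be later than the end date, and the event is not treatment-emergent.*
2. Add the same end-date check to SAP 5.3.2.3, so that a drug stopped before dosing is not given a start at first dose.
3. Replace SAP 5.3.2.1 with a reference to 5.4, which removes the circular restriction to TEAEs and the duplicate rule.
4. Align the Induction and whole-study TEAE definitions in SAP 3.7.2 on *on or after*, as in Protocol 8.8.2. This should accompany step 1; without the end-date check it would bring the misclassified events into the Induction tables.

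The cost is a few sentences in the SAP and one programming condition in each of the AE and medication derivations. No new data are needed. If the SAP is already final, its introduction provides for substantial modifications to be described in the clinical study report.

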8.8.2. Adverse Events

AEs will be coded to the preferred terms of the Medical Dictionary for Regulatory Activities (MedDRA®). Summaries will present by system organ class (SOC), preferred term (PT), and severity (mild, moderate, severe) the number and percentage of subjects for whom events were reported.

In general, a treatment-emergent adverse event (TEAE) will be defined as any AE that begins on or after the date and time of the first dose of study drug and up to the date of last dose of study drug plus the number of days in the follow-up period.

TEAEs will be summarized separately for the Induction and ATE phases. Assignment of TEAEs to different phases of the study (Induction or ATE) will be detailed in the SAPs.

All AEs will be listed by subject. The number and percentage of subjects who experience TEAEs will be summarized. Summaries of TEAEs will include the following types of summaries:

- All AEs, by SOC and PT and also by PT (by descending overall frequency)
- All AEs, by SOC, PT, and severity
- All study drug-related AEs, by SOC and PT
- All study drug-related AEs, by SOC, PT, and severity
- All AEs leading to premature discontinuation of study drug, by SOC and PT
- All AEs leading to temporary interruption of study drug, by SOC and PT
- All SAEs, by SOC and PT
- All study drug-related SAEs, by SOC and PT

A listing will be provided for all subjects who experience an SAE. Listings will also be provided for subjects who discontinued study treatment prematurely because of AEs and subjects who temporarily interrupted study treatment because of AEs. AEs of Special Interest, as described in Section 7.1.4, will be listed and summarized.

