All subjects who complete Induction at the Week 12 visit will continue into ATE, ATE Day 1 is scheduled for between 1 and 7 days after the Induction Week 12 visit where subjects will be treated with either 80 mg or 200 mg of TD-1473 for 48 weeks. Dose during ATE depends on treatment assignment during Induction (Figure 1 and Table 2): those who were dosed with TD-1473 during Induction will stay on the same dose; those who were dosed with placebo during Induction will be dosed with TD-1473 at 80 mg.

Table 2: Induction and Active Treatment Dose Assignment

Induction Dose (3:3:2 randomization)	Active Treatment Extension (ATE) Dose
80 mg	80 mg
200 mg	200 mg
Placebo	80 mg

During ATE, subjects will undergo clinic study visits every 4-12 weeks. Subjects will continue to complete a daily diary.

Subjects who have not shown clinical improvement (as assessed by the investigator) 16 weeks after initiation of ATE (i.e., ATE Week 16) will be discontinued from the study following completion of an End of Study (EOS) visit.

End of Study (EOS) Visit:

An EOS visit will be required for all subjects 4 weeks following their last dose of study drug. Subjects who complete an Early Study Drug Discontinuation visit during Induction or ATE will also be required to return for an EOS visit.

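### Incomplete AE onset dates are never compared with ATE Day 1, so an event that began after the switch to TD-1473 80 mg can be counted in the placebo Induction column

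*SAP*

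**What the plan says.** **Imputation rules.** SAP 5.4 treats incomplete onsets as follows, with first dose as the only reference point:

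- Month and year known, not the first-dose month: "impute AE onset as AE onset year and month with 01 as the date and 00:00 as the time".
- Year only, not the first-dose year: "impute AE onset as Jan. 1 of the AE onset year and 00:00 as the time".
- Complete date, no time, not the first-dose date: midnight at the start of that date.
- Month or year matching first dose, or onset wholly missing in most cases: the time of first dose.

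SAP 5.3.2.1 has a parallel rule for treatment-emergent events, the later of two dates: "the imputed day will be the first day of the month or the initial dosing date". It does not mention ATE Day 1 either.

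**Phase boundary.** SAP 3.7.2 counts an event as Induction if it starts after first dose and "up to the date/time of ATE Day 1 dose or date of last dose of study drug" plus 28 days, whichever comes first.

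**What happens at the boundary.** ATE Day 1 falls 1 to 7 days after the Week 12 visit. SAP 1.2.1 says that "those who were dosed with placebo during Induction will be dosed with TD-1473 at 80 mg", while the other two groups keep their dose. Protocol 8.8 summarises Induction safety by the treatment received in Induction.

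**Who was to supply the rule.** Protocol 8.8.2: "Assignment of TEAEs to different phases of the study (Induction or ATE) will be detailed in the SAPs". The readable SAP gives the window but says nothing about incomplete dates at the switch.

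**The concern.** The plan has two treatment boundaries, and its date rules respect only one. Completing a partial date with the earliest possible day guards against losing treatment-emergent events at first dose. At the second boundary the same habit moves events backwards, across a change of treatment. For a subject who took placebo in Induction, an event that began on TD-1473 80 mg can then be reported as a placebo event.

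Induction is the only placebo-controlled part of the trial, and safety is a primary objective. The placebo Induction column should contain only events that began before the switch.

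**Working it through.** The plan states no figure on this point, so there is none to reproduce. The check applies the SAP 5.4 rules to the SAP 3.7.2 window.

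**1. Two worked cases (illustrative dates, ATE Day 1 set 86 days after first dose)**

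| Case | First placebo dose | ATE Day 1 | True onset | Recorded as | Imputed onset | Counted in |
|---|---|---|---|---|---|---|
| Month only | 20 Feb 2020 | 16 May 2020 | 25 May 2020, on 80 mg | May 2020 | 1 May 2020, 00:00 | Induction, placebo |
| Year only | 20 Nov 2019 | 14 Feb 2020 | 15 Sep 2020, on 80 mg | 2020 | 1 Jan 2020, 00:00 | Induction, placebo |

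The month-only result does not depend on the day of the switch: if ATE Day 1 is itself the 1st, midnight still precedes the dose. The year-only result needs 1 January to fall between first dose and ATE Day 1. If the switch was already made in the earlier year, 1 January falls in the extension and the assignment is correct.

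**2. Missing time on the ATE Day 1 date.** Protocol 6.3.7 has the ATE Day 1 dose given in clinic in the morning. An event later that day with no recorded time is set to midnight, before the dose, and so counts as Induction. Protocol 7.3 lists onset and resolution dates among the recorded items and does not mention times. For the first-dose date SAP 5.4 does substitute the dose time; there is no equivalent for ATE Day 1.

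**3. Enumeration.** First-dose dates covered every day of one year; ATE Day 1 was 84, 87 or 93 days later; true onset was uniform over 48 weeks plus 28 days after the switch (336 + 28 = 364 days).

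- Month-only onsets in the ATE Day 1 month: 5,395 of 5,395 placed in Induction at the 84-day lag; likewise all at the other lags.
- Share of all post-switch month-only onsets: 5,395 / (365 × 364) = 4.1%.
- Mean post-switch days in the switch month: 5,395 / 365 = 14.8.
- Year-only onsets placed in Induction by the 1 January rule: 20% to 22%.
- True Induction onsets pushed past ATE Day 1: 0%. The shift runs one way.

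**4. Expected count, switch-month case, placebo column.** The documents give neither a partial-date rate nor an event rate. Assumed: 1-5% of onsets partial, 3-6 events per subject-year, all 40 planned placebo subjects entering the extension.

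- Exposure: 40 × 15 days = 600 subject-days; 600 / 365.25 = 1.64 subject-years.
- Events: 1.64 × 3 = 4.9 to 1.64 × 6 = 9.9.
- With a partial date: 4.9 × 0.01 = 0.05 to 9.9 × 0.05 = 0.5.

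**5. Expected count, missing-time case.** If no times were recorded at all: 40 × 1 day / 365.25 = 0.11 subject-years, giving 0.33 to 0.66 events on the ATE Day 1 date at the same flat rates. Some of these would truly precede the dose.

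**6. Size of one misplaced subject.** 1/40 = 2.5 percentage points, if that subject was not already counted in the same row. SAP 3.7.2 counts a subject once per preferred term.

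**The case against.** The strongest reply is that the rule is common to all arms. Subjects on 80 mg and 200 mg also have partially dated early-extension events pulled into Induction. After the switch, former placebo subjects and the 80 mg group take the same dose, so the expected addition per subject is about equal and the 80 mg minus placebo difference barely moves. This stands. A reader might infer that the rule hides a drug effect. The documents do not support that: it would require new starters to have more early events than subjects continuing on drug, and nothing in the plan shows this.

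A reader might also infer that about half of all year-only onsets are misplaced, because 28 to 30 further points in the enumeration come from the rule that begins "If AE onset date has year only and it is year of first dose of study drug, then impute AE onset as date/time of first", and that wholly missing onsets all join them through "Else if AE IS ongoing and AE onset date missing, then impute AE onset as date/time of first study drug dose". That goes too far. Those events are set exactly to first dose, and SAP 3.7.2 starts Induction after first dose. Read literally, they fall outside the Induction table. That is a separate wording gap, and nothing here relies on it.

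Third, events are asked about at every visit, including ATE Day 1 and ATE Weeks 4, 8 and 16, and serious events and most events of special interest are reported within 24 hours. A post-switch event known only by year should be rare. This also stands. In addition, the study was to stop early, so the 4.1% share, which assumes full extension follow-up, is only indicative; the switch-month count in step 4 does not use it.

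Finally, all events are listed by subject, so an attentive reader could find the affected ones. That helps disclosure but does not correct the table. Parts of the later SAP are blacked out; no visible heading or cross-reference points to a further rule for these dates.

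**Conclusion.** The point holds as a minor defect. The written rules place certain post-switch events in Induction, always in the same direction, and in the placebo column this attributes drug-exposed events to the wrong treatment. In the active columns the phase is wrong but the dose is right.

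The expected effect is well under one placebo event for partial dates in the switch month (about 0.05 to 0.5), and also below one for missing times on ATE Day 1 at a flat event rate. Both figures rest on assumed partial-date and event rates and on the planned group size. The effect on the comparison of 80 mg with placebo is smaller still, because the arms shift together. The case for changing the rule is correct labelling of a small placebo column, not a material bias in the safety conclusion.

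**What to change.** Apply the following identically in all three arms.

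1. In SAP 5.3.2.1 and 5.4, when an incomplete onset is compatible with both sides of the ATE Day 1 dose, use the event end date first, and the visit at which the event was first recorded if that is captured.
2. If it is still ambiguous, including a missing time on the ATE Day 1 date, set onset to the date and time of the ATE Day 1 dose. In SAP 3.7.2, state that Induction events start before that dose; under the present upper limit an onset equal to the dose time could still be read as Induction. Such events then leave the Induction table and stay in the overall-study table.
3. List the affected events and give the Induction count under both assignments.

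A default confined to former placebo subjects should be avoided: it would remove true late-Induction events from the placebo column while keeping identical ones in the active columns.

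Cost: a few sentences, one programming check and one short listing. No new data are needed, since the end date is already collected and the visit of first recording is optional. The drawback is that some true late-Induction events will leave the Induction table in every arm (about half of an average switch month lies before the switch). The count under both assignments shows how many events are involved.
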